12.4 Primary Endpoint

The primary efficacy endpoint is to generate effect sizes for changes in the number of impaired neuropsychological tests. The planned intervention period is three months. Neuropsychological outcomes will be examined using a 2 (group; COGNUTRIN, placebo) X 2 (time; baseline, three-months) repeated measures ANOVA to examine differences in the number of impaired neuropsychological tests. Age, premorbid cognitive functioning, depression and fatigue will be evaluated for association with neurocognitive performance and entered as covariates in statistical analyses if a marginally significant association ($p < .10$) is observed.

The primary efficacy endpoint is to generate effect sizes for changes in the number of impaired neuropsychological tests. The planned intervention period is three months. Neuropsychological outcomes will be examined using a 2 (group; COGNUTRIN, placebo) X 2 (time; baseline, three-months) repeated measures ANOVA to examine differences in the number of impaired neuropsychological tests. Age, premorbid cognitive functioning, depression and fatigue will be evaluated for association with neurocognitive performance and entered as covariates in statistical analyses if a marginally significant association ($p < .10$) is observed. The sample size of 20 patients per arm will allow us to generate useful information for future studies, in terms of anticipated effect size. Although this pilot study is not designed to be fully powered, the current sample size will allow us to detect an effect size difference of .40 for a one-tailed paired sample t-test, on account of the matched groups, at power of .80 and an alpha of .05. Moreover, the sample sizes will enable us to detect a group X time interaction of .23, with an alpha of .05, power of .80, and a stability coefficient of .5.

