Cognitive performance will be obtained using a battery of valid and reliable cognitive performance tests has been selected for administration based on the results of preliminary studies and previous research on the impact of cognitive training and nutritional supplementation on cognitive performance in older adults as well as previous research on cognitive deficits in breast cancer survivors. The tests will be used to derive composite indices for the domains of memory, executive functioning, processing speed, visual-spatial ability, and attention/concentration. The assessment of each domain with multiple measures is designed to more fully represent the domain and to minimize the possibility that scores reflect idiosyncratic performance on a single test. The assignment of measures to domains is based on accepted descriptions of their functional demands. We recognize that these measures are not pure tests of a domain and that some measures may draw on multiple domains. Nevertheless, the assignment of measures to domains as organized below can be considered a useful heuristic for characterizing cognitive functioning. To ensure the quality of the data collected, these tests will be administered and scored only by research personnel at Moffitt Cancer center qualified and trained by Drs. [name] and [name] before the start of the study and supervised by them during the course of the study.

Cognitive Status. Mini-Mental State Examination, (MMSE) (Appendix IX). This domain will be used to screen for and estimate the severity of cognitive impairment in order to determine participant's eligibility to participate in the study. The MMSE has demonstrated validity and reliability in psychiatric, neurologic, geriatric, and other medical populations.

Estimated Intellectual Ability. The Wechsler Test of Adult Reading (WTAR) ¹²⁷ (Appendix X) requires participants to pronounce 50 irregular words that cannot be easily decoded phonetically. Previous studies have shown that performance on the NART is highly correlated with general intelligence (factor 'g') as measured by the Wechsler intelligence scales ¹²⁷. (Accordingly, the WTAR will be administered to all participants at baseline only to obtain an estimate of overall intellectual ability). WTAR scores will be used for descriptive purposes and as a covariate in all analyses comparing cognitive performance in the study samples.

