7.7.13 Inflammatory markers-Cytokines will be measured with a panel including IL-1, IL-4, IL-6, IL-8, IL-10, IL-12, GM-CSF, IFN-gamma, TNF α , and CRP (BioRad-Bioplex). All of these biomarkers have been shown to increase with disease, aging and cytotoxic agents and will be used to monitor compliance with the dietary supplementation group and as a covariate in the analysis of cognitive function. The cytokine panel will be completed by [name] in her research laboratories.

One 10 ml of blood will be collected in a purple top (EDTA) vacutainer and centrifuged at 3000 RPM /10 minutes/ RT for isolation of PBMC, plasma and RBC. Approximately 5 ml of plasma will be collected and placed into one labeled screw cap tube and frozen at -80C. The Buffy Coat with adjacent layer of plasma & RBC will be harvested and transferred to 50 cc conical tube with 10ml of PBS. The remaining RBC will be harvested and washed 3 times with PBS and then re-suspended in equal volume of distilled water. Two, 1 ml RBC aliquots will be placed in labeled screw cap tubes and frozen in at -80C. Harvested BC will be harvested on Ficoll for PBMC (no cell count required). PBMC will be washed once in PBS and the cells will then be re-suspend in 2ml of Freezing Media (40 ml FBS + 7 ml DMSO + 3 ml RPMI). Two, 1ml aliquots of PBMC will be placed in labeled cryovials, and frozen MR. Once frosty, they will be placed in storage. All samples will be stored in the Tissue Core at Moffitt Cancer center until analysis.

2 - 10 ml tube will be forwarded to Tissue Core labs at the Moffitt Cancer Center for processing and storage. Once labs specimens for 40 subjects (pre and post intervention) have been collected, they will be transported from Tissue to [name] lab at USF and [name] lab at MCC by the clinical research coordinators, using appropriate containers to preserve the temperature and thus integrity of the specimens for assay of oxidative stress markers.

The plasma collected for assay of oxidative test markers and cytokines will be stored for a maximum of 12 months at -80°C. All specimens collected for assay of safety markers (CBC, CMP, PT, PTT, and LDL) will not be stored as they will be completed in real time.

7.7.14 Magnetic Resonance Imaging: Structural and Resting-state functional MRI (fMRI):

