8.1 Primary Endpoint

The primary efficacy endpoint is to generate effect sizes for changes in the number of impaired neuropsychological tests. The planned intervention period is three months. Neuropsychological outcomes will be examined using a 2 (group; COGNUTRIN, placebo) X 2 (time; baseline, three-months) repeated measures ANOVA to examine differences in the number of impaired neuropsychological tests. Age, premorbid cognitive functioning, depression and fatigue will be evaluated for association with neurocognitive performance and entered as covariates in statistical analyses if a marginally significant association ($p < .10$) is observed.

The primary safety endpoint is incidence and severity of AEs occurring during intervention with either COGNUTRIN or placebo. All AEs that are reported by the subject, detected during a visit, physical examination, or laboratory work-up will be recorded in the participant's medical record and recorded on the CRF. All AEs that occur after the informed consent is signed will be recorded on the AE CRF whether or not related to study agent.

The sample size proposed in the current protocol will not provide sufficient statistical power, but information regarding effect sizes will be gathered and used as motivation for future clinical trials. We estimate that a minimum evidence of improvement in cognitive function with the 3 month intervention as indicated by a score of 1 standard deviation or more above population norms on the Hopkins Verbal Learning Test – Revised, Controlled Oral Word Association Test, or Color Trails Test Part 1 or 2 will be considered adequate to justify progression to a larger study.

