8.2 Secondary Endpoints

The secondary endpoint will be improvement in subjective cognitive functioning as well as structural and resting state functional changes in MRI.

In addition we will examine the role of the cytokines and anti-oxidant biomarkers as mediators of reductions in the number of impaired cognitive tests.

We will also examine if other factors such as fatigue, depression, physical and functional activities are affected by COGNUTRIN compared to placebo.

The sample size proposed in the current protocol will not provide sufficient statistical power, but information regarding effect sizes will be gathered and used as motivation for future clinical trials.

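### The primary 2x2 ANOVA is valid but less precise than ANCOVA at the plan's own r = .5, and its covariate rules conflict on WTAR and leave the covariate visit unstated

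*Combined protocol and SAP*

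**What the plan says.** Sections 8.1 and 12.4 give the same primary analysis: "Neuropsychological outcomes will be examined using a 2 (group; COGNUTRIN, placebo) X 2 (time; baseline, three-months) repeated measures ANOVA". The outcome is the number of impaired tests, and the stated purpose is to generate effect sizes. The baseline count is not entered as a covariate anywhere.

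The covariate rule in 12.4 is "Age, premorbid cognitive functioning, depression and fatigue will be evaluated for association with neurocognitive performance and entered as covariates in statistical analyses". Section 8.1 repeats it: "entered as covariates in statistical analyses if a marginally significant association", with p < .10 as the threshold. Section 12.5.4 applies the same threshold to psychotropic medication.

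Two other sections also set covariates:

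- Section 7.7.9: "WTAR scores will be used for descriptive purposes and as a covariate in all analyses comparing cognitive performance in the study samples". It adds that "the WTAR will be administered to all participants at baseline only to obtain an estimate of overall intellectual ability".
- Section 7.7.13, on the cytokines: "will be used to monitor compliance with the dietary supplementation group and as a covariate in the analysis of cognitive function". Section 8.2, however, plans to examine the "role of the cytokines and anti-oxidant biomarkers as mediators of reductions in the number of impaired cognitive tests", and 12.5.1 specifies changes in the biomarkers as the mediator.

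The power statement in 12.4 gives a detectable group by time interaction of .23 for 20 patients per arm, "with an alpha of .05, power of .80, and a stability coefficient of .5".

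**The concern.** The main product of this pilot is one effect estimate with its interval, to be used in planning a larger trial. Two things weaken it.

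First, the planned model does not use the baseline count as efficiently as it could. A change-score analysis fixes the slope of follow-up on baseline at 1, although the plan itself assumes a correlation of .5.

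Second, the adjusted model cannot be determined from the document. Two sections disagree on whether WTAR is always in the model. For depression, fatigue, medication and cytokines, nothing says which visit's value is the covariate, or at which visit the p < .10 association is tested. The model would have to be settled after the data are seen.

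**Working it through.** **Inputs.** From 12.4: 20 per arm (N = 40), interaction .23, alpha .05, power .80, stability coefficient .5. From 4.3: 10% loss, leaving 36. Readings and assumptions: .23 is Cohen's f; the stability coefficient is the correlation r between baseline and three-month counts; the SD is the same at both visits; the count is roughly normal (relaxed in step 4).

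**Step 1: reproduce the plan's figure.** For a 2x2 within-between interaction, lambda = f² x N x 2/(1 - r) = 0.23² x 40 x 2/0.5 = 8.46. With 1 and 38 df the power is 0.809, so the stated .80 reproduces. The f that gives exactly .80 is 0.227. On the outcome scale the between-arm difference in change is 4f, so 0.227 corresponds to 0.91 SD.

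**Step 2: variance of the two analyses, in units of the outcome variance.** With two time points the interaction F is the square of the two-sample t on change scores.

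- Change score: 2(1 - r) = 2 x 0.5 = 1.000.
- ANCOVA with k covariates besides arm: (1 - r²)(N - 3)/(N - 3 - k). The last factor is the cost of estimating the slopes, taking any covariate beyond the baseline count as not prognostic.
- Baseline count only (k = 1): 0.75 x 37/36 = 0.771, a saving of 22.9%.
- Baseline count, age and WTAR (k = 3): 0.75 x 37/34 = 0.816, a saving of 18.4%.

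The standard error is the square root of (variance x 2/20). Results at r = .5:

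| Analysis | Residual df | SE (SD units) | 95% CI half-width | Detectable at 80% power |
|---|---|---|---|---|
| Change score | 38 | 0.316 | 0.640 | 0.909 |
| ANCOVA, baseline only | 37 | 0.278 | 0.563 | 0.799 |
| ANCOVA, baseline + age + WTAR | 35 | 0.286 | 0.580 | 0.823 |

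**Step 3: dependence on r.** Variance saving over change scores:

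| Model | r = .5 | r = .7 | r = .8 |
|---|---|---|---|
| Baseline only, N = 40 | 22.9% | 12.6% | 7.5% |
| + age + WTAR, N = 40 | 18.4% | 7.5% | 2.1% |
| + age + WTAR, N = 36 | 17.5% | 6.5% | 1.0% |

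If age and WTAR each correlate .3 with both scores (assumption), the three-covariate saving at r = .5 is 22% to 24%.

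**Step 4: bounded count.** Counts were simulated from 8 or 12 test scores, each impaired at 1 SD or more below the norm, with an assumed between-test correlation of .35. The three-covariate model saved 15% to 20% when r was .49 to .55. At r of .82 to .86 the result ran from a 3% saving to a 2% loss. Type I error was 4.6% to 5.1%.

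**Step 5: the covariate rules side by side.**

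- WTAR: 7.7.9 includes it always; 8.1 and 12.4 include premorbid functioning only if p < .10. Both cannot be followed if the terms mean the same thing. That they do is an inference, but a natural one: WTAR is the only estimate of intellectual ability in the battery.
- Visit: Table 1 and 7.7.10 place PHQ-9 and FSI at baseline and week 12. Table 1 places the cytokines at screening and week 12. Section 12.5.4 records medication at baseline and during the study. No rule chooses among these values. Age and WTAR raise no such question.
- Cytokines: a baseline level as covariate (7.7.13) and change as mediator (8.2, 12.5.1) can coexist. A post-treatment level as covariate would not fit, because it would adjust away part of the effect that the mediation analysis sets out to explain. The plan does not say which is meant.

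**The case against.** The strongest reply is that the planned test is sound, its interaction power statement reproduces, and the pilot says openly that it is not fully powered. Moving the CI half-width from 0.64 to 0.58 SD changes little in practice. The .5 is a power input, not an estimate for this count, and near r = .8 the gain almost disappears. All of this stands. It limits the size of the point but does not remove it, since the improvement needs no new data and the WTAR contradiction has to be resolved under either model.

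A reader might infer more than the documents support:

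- *That the ANOVA is biased or invalid.* It is not: in simulation both analyses held type I error at about 5.1%.
- *That 7.7.13 contradicts 8.2 and 12.5.1.* It is an ambiguity, resolved if the covariate is the baseline value.
- *That week-12 values will be used as covariates.* No section says so; none rules it out. Any figure for the resulting harm would rest wholly on assumed inputs.
- *That the p < .10 screen costs a known amount of precision.* Its direction depends on the assumption. With four covariates correlated .3 with both scores, the change-score variance was multiplied by 1.08. With .3 at baseline and .1 at follow-up the factor was 0.98. In the first setting type I error stayed at 5.0% to 5.2%. The case against the screen is that it leaves the model open.
- *That the schema and 7.3 give conflicting visit orders which undermine the baseline values.* Neither list is stated to be chronological, and a before-first-dose rule works in either order.

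**Conclusion.** The point holds as one of efficiency and pre-specification. At the plan's r = .5 and N = 40, adjusting for the baseline count saves 23% of the variance, or 18% with age and WTAR added and not prognostic. The detectable difference falls from 0.91 to 0.80 or 0.82 SD. These figures assume equal SDs and approximate normality, and the count simulation gives similar savings at r near .5. If the true r is near .8, the recommended model gains almost nothing.

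The conflict between 7.7.9 and 8.1/12.4 over WTAR is real on the natural reading of premorbid functioning. The missing visit for depression, fatigue, medication and cytokine covariates is a gap that should be closed before analysis. The progression rule in 8.1 and 12.7 uses other criteria and is unaffected.

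**What to change.** In 8.1 and 12.4, replace the ANOVA and covariate sentences with wording to this effect:

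> The primary analysis is a linear ANCOVA of the three-month number of impaired tests on arm, with baseline number of impaired tests, age and WTAR as fixed covariates. We will report the adjusted difference with its 95% CI and a bootstrap 95% CI, a standardized effect, the SD, and the correlation between baseline and follow-up. Only values obtained before the first dose of study agent may be covariates.

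Then:

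- Drop the p < .10 screen for the primary model (8.1, 12.4, and 12.5.4 where it bears on that model).
- Put baseline PHQ-9, one named baseline FSI score and baseline psychotropic medication (yes/no) in one sensitivity model.
- Keep radiation and endocrine therapy, which 12.3 balances, out of the primary model and add them in a sensitivity analysis. If not prognostic, adding them to the three covariates cuts the saving at r = .5 to 13% (0.75 x 37/32 = 0.867) and gives a 4% loss at r = .8 (0.36 x 37/32 = 0.416 against 0.400).
- Keep the WTAR sentence in 7.7.9.
- In 7.7.13, state that any cytokine covariate is the baseline value and that change is used only in the mediation analysis.
- In 12.4, label the .23 interaction figure as referring to the change-score test, or restate it for the ANCOVA: about 0.82 SD at 80% power with r = .5, 20 per arm, and age and WTAR not prognostic.

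The cost is analysis wording only, since every variable is already collected. The downside is three residual degrees of freedom (35 against 38) and almost no gain if r is near .8.

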The research staff will use the Demographic Questionnaire Form to obtain baseline demographic data, medical and family history, and information regarding other health habits such as alcohol, tobacco and previous nutritional supplement use. Clinical Research Form (CRF): All medical record data (CRF) pertaining to the cancer diagnosis, tumor characteristics, node involvement, stage confirmation, medical history of cancer, menstrual cycle information, other medical history including renal or liver disease, concomitant medications including treatments for cancer and autoimmune diseases will be obtained from all subjects at baseline and changes in these variables monitored. Once clinical eligibility is confirmed, and informed consent is signed, randomization of subjects takes place within the Moffitt SRARS program. SRARS is a web delivered application that records subject registrations and provides randomization assignments. Subjects will be randomized to one of 2 groups. An email is sent to a list of pre-determined recipients (clinical research coordinators) stating the treatment/randomization assigned to the subject.

5.9 Blinding and Unblinding Methods: All requests to unblind treatment assignment will be directed to the Protocol Lead Investigators ([name], Moffitt Cancer Center & Research Institute, [contact], [contact], e-mail: [contact] . [name] will determine if disclosure of treatment assignment is required after consultation with the Medical Doctor who is the primary MD for the subject. If disclosure of the treatment would affect important medical decisions in a subject experiencing an AE, or could affect decisions regarding safe conduct of the clinical trial, unblinding might be allowed. If disclosure is warranted, the site will be directed to the product label found in the subject's CRF binder or other designated research record. The label has a scratch-off area that will disclose the treatment assignment. Each site will document the unblinding process in the patient chart.

6. AGENT ADMINISTRATION:

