12 STATISTICAL CONSIDERATIONS

12.1 Study Design/Endpoints

The central hypothesis for this Pilot clinical trial is that adults who receive COGNUTRIN will exhibit reduction in the number of impaired cognitive tests, as compared to adults on the placebo.

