12.2 Sample Size/Accrual Rate

In this pilot trial, we plan to accrue 40 evaluable subjects. This is a feasibility clinical trial in preparation to inform the design of a well-powered randomized clinical trial.

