12.3 Randomization and Stratification

During the baseline/randomization visit, subjects will be randomized using block randomization. The current design will ensure equal number of subjects in each arm receiving radiation therapy post chemotherapy and concurrent endocrine therapy.

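### Section 12.4 claims 80% power at .40 from a paired t-test on matched groups, but no women are matched; the randomised 20 versus 20 comparison has 34% (one-sided) or 23% (two-sided) power at 0.40 SD of change

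*Combined protocol and SAP*

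**What the plan says.** Section 12.1 states a between-arm hypothesis: "adults who receive COGNUTRIN will exhibit reduction in the number of impaired cognitive tests, as compared to adults on the placebo". Section 5.8 describes the allocation: "Subjects will be randomized to one of 2 groups". Section 12.3 adds that "subjects will be randomized using block randomization", with the arms balanced on receipt of radiation and endocrine therapy. Section 12.2 gives the size: "we plan to accrue 40 evaluable subjects".

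The planned primary analysis in section 12.4 is a 2 (group) by 2 (time) repeated measures ANOVA on the number of impaired tests. The same section says "The sample size of 20 patients per arm will allow us to generate useful information for future studies" and then makes two sensitivity claims:

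- The sample can "detect an effect size difference of .40 for a one-tailed paired sample t-test, on account of the matched groups, at power of .80", with alpha .05.
- In addition, "the sample sizes will enable us to detect a group X time interaction of .23", with alpha .05, power .80 and a stability coefficient of .5.

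Both claims follow an acknowledgement that the pilot is not fully powered. Section 8.1 is blunter: "The sample size proposed in the current protocol will not provide sufficient statistical power".

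**The concern.** A paired t-test between arms needs each COGNUTRIN woman linked to a particular placebo woman. Balancing the arms on two treatment factors makes the groups similar in composition but links no individuals. No section of the current text forms pairs, and the planned analysis does not use any.

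The pilot exists to supply effect-size information for a larger trial. A reader who trusts the .40 statement could take a null result as evidence against an effect of 0.40 SD, or carry the paired, one-tailed reasoning into the next sample size calculation. The unlabelled .23 adds to the risk: read as SD units, it suggests the trial is sensitive to even smaller effects.

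**Working it through.** **Inputs.** 20 per arm and 40 evaluable in total (sections 12.4 and 12.2); effect .40, alpha .05, power .80, one-tailed (12.4); interaction .23 with correlation .5 (12.4); two randomised arms without pairing (5.8 and 12.3). Section 12.4 does not say which SD the .40 refers to.

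**1. Reproduce the .40 claim as written.** For a paired t-test with n pairs, df = n − 1 and the noncentrality is d√n. One-sided, alpha .05:

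| Pairs | Noncentrality at .40 | Power at .40 | d for 80% power |
|---|---|---|---|
| 40 | 0.40 × √40 = 2.53 | 0.7997 | 0.400 |
| 20 | 0.40 × √20 = 1.79 | 0.532 | 0.577 |

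The stated power comes from n = 40. Forty women give 40 pairs only if each is paired with her own baseline and the arms are pooled. Had the arms been truly matched, there would be 20 pairs and 53% power.

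**2. The comparison the trial actually makes.** For two independent arms of 20, df = 38 and the noncentrality is d × √(20 × 20 / 40) = d√10. At d = 0.40 it is 0.40 × √10 = 1.26.

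| | One-sided | Two-sided |
|---|---|---|
| Power at 0.40 SD of change | 34.4% | 23.4% |
| Effect for 80% power (SD of change) | 0.801 | 0.909 |
| Per arm for 80% power at 0.40 | 78 | 100 |

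**3. The group-by-time figure.** Take .23 as Cohen's f. The noncentrality of F(1, 38) is f² × N × 2 / (1 − ρ) = 0.23² × 40 × 2 / 0.5 = 8.464, which gives power 0.809. Exactly 80% power is reached at f = 0.227, which rounds to the stated .23. To convert, equate 160f² with the squared two-sample noncentrality 10d², so d = 4f. Then 4 × 0.227 gives 0.909 SD of change, which agrees with the two-sided entry in step 2 (the rounded .23 itself gives 0.92). The ANOVA figure is therefore correct, and it implies a detectable difference more than twice .40.

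**4. Assumption ranges.** In baseline SD units with equal variances, the two-sided detectable effect is 0.909 × √(2(1 − ρ)):

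- ρ = .3: 1.08
- ρ = .5: 0.91
- ρ = .7: 0.70
- Baseline-adjusted analysis at ρ = .5 (df = 37, residual SD √(1 − .5²)): 0.79

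If .40 is in outcome SDs and ρ runs from 0 to .8, power at .40 is:

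- Change score: 22% to 63% one-sided, 14% to 50% two-sided
- Baseline-adjusted: 34% to 67% one-sided, 23% to 54% two-sided

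None of these reaches 80%.

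**5. If 40 is the number randomised.** Section 5.8 sets a minimum of 40 randomised and section 4.3 expects 10% loss, which would leave 18 per arm. Power at 0.40 SD of change falls to 32.0% one-sided or 21.5% two-sided, and 80% power needs 0.846 or 0.961 SD.

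**The case against.** The strongest reply is that .40 is not a miscalculation. It reproduces for 40 pairs, and if read as an unlabelled Cohen's f for two independent arms it equals 2 × 0.40 = 0.80 SD, which is the correct one-sided detectable effect. That reading would also put .40 on the same scale as .23. It remains a possible account of where the number came from. But the sentence names a paired test, calls the quantity an effect size difference and justifies it by matching, and that justification fails on any scale.

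Second, the plan says one-tailed and the hypothesis is directional, so 34% is the like-for-like figure and 23% reflects a change of sidedness. That is fair. The two-sided figure is still relevant because the planned ANOVA F test is non-directional.

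Third, little hangs on the number. Sections 8.1, 8.2 and 12.4 disclaim adequate power, and the progression criterion in sections 8.1 and 12.7 does not use .40. This stands and limits the seriousness. It does not rescue the sentence, because a general disclaimer followed by a specific power figure leaves the reader with the figure.

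Fourth, the scale of .23 can be recovered from the alpha, power, correlation and sample size given. True, but only by recalculation, and a label would spare the reader that.

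**Conclusion.** The concern holds. The design does not have the power stated in section 12.4 for an effect of .40. With 20 evaluable women per arm and an unadjusted change score, power at 0.40 SD of change is 34% one-sided or 23% two-sided, and the effect detectable with 80% power is 0.80 or 0.91 SD. The exact figures depend on the SD scale and on the correlation between baseline and three months, but no correlation from 0 to .8 brings power at .40 to 80%, with or without baseline adjustment. The .23 figure is correct as Cohen's f and lacks only its label. Because the pilot disclaims full power and no decision rule depends on .40, this is a statement that should be corrected; it is not a flaw in the size of the trial.

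**What to change.** In section 12.4, delete the statement built on .40, the one-tailed paired test and matched groups. Replace both power statements with wording such as:

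> With 20 evaluable participants per arm (two-sided alpha .05, power .80, correlation .5 between baseline and 3 months), the unadjusted group × time test can detect Cohen's f = .23, i.e. a between-arm difference in change of about 0.91 SD of the change score.

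If 40 is the number randomised and 10% loss is expected, quote the 18-per-arm value instead: 0.96 SD of change, or f = 0.961 / 4 = 0.24.

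The cost is a wording amendment. No patients, visits or analyses are added. The stated sensitivity becomes less favourable, and it will match the planned analysis.

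### The detectable effect of .40 in Section 12.4 is for a one-tailed paired t-test, not for the planned between-arm test, which with 20 per arm detects about 0.91 SD of change

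*Combined protocol and SAP*

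**What the plan says.** Section 12.1 frames the hypothesis as a comparison between arms, with a direction: "adults who receive COGNUTRIN will exhibit reduction in the number of impaired cognitive tests, as compared to adults on the placebo". Section 12.4 sets an estimation aim, "The primary efficacy endpoint is to generate effect sizes for changes in the number of impaired neuropsychological tests", and names one analysis: "Neuropsychological outcomes will be examined using a 2 (group; COGNUTRIN, placebo) X 2 (time; baseline, three-months) repeated measures ANOVA". Section 8.1 names the same analysis. Neither section states the sidedness of the test or asks for a confidence interval on the primary effect.

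Section 12.4 then closes with two detectable effects for 20 patients per arm:

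- The first is to "detect an effect size difference of .40 for a one-tailed paired sample t-test", justified "on account of the matched groups, at power of .80 and an alpha of .05".
- The second is to "detect a group X time interaction of .23, with an alpha of .05, power of .80, and a stability coefficient of .5".

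Section 12.3 describes block randomisation that balances the arms for radiation and endocrine therapy. It describes no one-to-one matching of patients.

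**The concern.** A detectable effect should belong to the test that will be run. The .40 figure differs from the planned test in two ways.

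- **Sidedness.** The .40 is labelled one-tailed. The interaction F-test has one numerator degree of freedom and is non-directional, so alpha .05 there is the same as a two-sided .05 t-test on change scores. Both figures print alpha .05, but the chance of a false positive in favour of COGNUTRIN is 5% for the first and 2.5% for the second.
- **Pairing.** A paired t-test needs differences within pairs. Two independently randomised arms give a two-sample comparison of changes. Balance on two treatment factors does not turn patients into pairs.

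The trial exists to inform a larger one. A reader who takes .40 at 80% power as the sensitivity of the COGNUTRIN-placebo comparison will think this pilot far more informative than it is, and may give a null or imprecise result too much weight when planning the next study.

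**Working it through.** **Inputs.** From Section 12.4: 20 per arm, alpha .05, power .80, effects .40 and .23, stability coefficient .5. From Section 12.2: 40 evaluable subjects. Assumption: .23 is Cohen's f, since Section 12.4 does not name the metric.

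**1. Reproduce .40.** For a paired t-test, df = n - 1 and the noncentrality is d x sqrt(n).

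| Paired differences | Sidedness | Noncentrality at d = .40 | Critical t | Power at .40 | Detectable d at 80% |
|---|---|---|---|---|---|
| 40 | one-tailed .05 | .40 x sqrt(40) = 2.530 | 1.685 | .800 | .400 |
| 40 | two-sided .05 | 2.530 | 2.023 | .694 | .454 |
| 20 | one-tailed .05 | .40 x sqrt(20) = 1.789 | 1.729 | .532 | .577 |

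Of these, only 40 differences with a one-tailed test returns the stated figure. Forty differences are available if every patient's own before-after change is pooled over both arms, but that is not a comparison of COGNUTRIN with placebo. Pairing patients across arms would give at most 20 differences.

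**2. Reproduce .23.** For the interaction, lambda = f² x N x m / (1 - r), with m = 2 times and df 1 and 38.

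- lambda = .23² x 40 x 2 / .5 = 8.464.
- Power at alpha .05 is .809; 80% power is reached at f = .227. So .23 fits the ordinary non-directional F-test at N = 40.
- At alpha .10, the equivalent of one-tailed .05, power would be .887 and the detectable f would be .200.

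**3. Put the planned test on the scale of a between-arm difference.** The interaction F equals the square of a two-sample t on change scores, with noncentrality d x sqrt(20/2) = d x sqrt(10).

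- Setting d² x 10 = f² x 160 gives d = 4f.
- f = .23 is d = 0.92, and f = .227 is d = 0.91 SD of change.
- With correlation .5, the variance of change is 2 x (1 - .5) = 1 times the score variance, so an SD of change equals an SD of the score at one visit.

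**4. Power of the planned contrast at 0.40.** The noncentrality is .40 x sqrt(10) = 1.265 with df 38.

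| Sidedness | Critical t | Power at 0.40 SD | Detectable at 80% |
|---|---|---|---|
| two-sided .05 | 2.024 (F = 4.10) | .234 | 0.909 SD |
| one-tailed .05 | 1.686 | .344 | 0.801 SD |

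Most of the gap between .40 and 0.91 comes from the pairing: even one-tailed, the two-arm contrast detects 0.80 SD. Sidedness accounts for the step from 0.80 to 0.91.

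**5. Precision.** The half-width of a 95% interval for the between-arm difference is 2.024 x sqrt(2/20) = 0.64 SD of change.

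**The case against.** The strongest reply is that the paired t-test is a sensitivity statement only. One analysis is planned, the endpoint is to generate effect sizes, Section 12.4 says that the pilot is not fully powered, and Section 8.1 says that the sample will not give sufficient power. Sections 8.1 and 12.7 rest progression on a score threshold against population norms, not on a test. A one-tailed figure also agrees with the directional hypothesis in Section 12.1, and its label is disclosed.

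Most of this stands, and it limits the consequence. A reader might infer that the plan sets two rival criteria, so that a result with two-sided p between .05 and .10 would be significant under one and not the other. The documents do not support that: the one-tailed test is never named as an analysis, it is paired and so not the same statistic as the between-arm contrast, and no decision hangs on a p-value. A reader might also think that a one-tailed criterion weakens the safety assessment. It does not, because the primary safety endpoint is the incidence and severity of adverse events, which Section 12.6 summarises separately.

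What the reply does not remove is the number itself. Section 12.4 states an effect size and a power as properties of this sample, and the planned comparison does not have them. Saying that a pilot is underpowered does not correct a stated figure that implies otherwise.

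**Conclusion.** The .40 figure is misstated for this design. At two-sided .05 with 20 per arm, the planned group x time contrast has about 23% power at 0.40 SD of change and detects about 0.91 SD at 80%. The interaction of about .23 that Section 12.4 already gives is the same quantity on another scale, so the two figures in that section do not describe the same sensitivity.

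This rests on 40 evaluable patients, .23 being Cohen's f, approximately normal changes, and no gain from covariates. The correlation of .5 is needed for the link to f = .23, but not for 0.91 SD of change. If the 10% loss in Section 4.3 left 36 evaluable, the detectable f would be .240, or 4 x .240 = 0.96 SD. The documents give no SD for the change in the number of impaired tests, so none of these figures can be converted to a number of tests.

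The planned analysis and the progression rule are untouched; this is a correction to a stated number and to an unstated sidedness.

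**What to change.** In Sections 8.1 and 12.4:

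1. Name the group x time effect, the COGNUTRIN minus placebo difference in change in the number of impaired tests, as the primary contrast. State two-sided alpha .05 and report the effect with a 95% confidence interval.
2. Delete the one-tailed paired t-test figure and its appeal to matched groups.
3. Restate the detectable effect for that contrast only: about 0.91 SD of change at 80% power with 20 per arm, equivalent to an interaction f of about .23 with N = 40 and correlation .5. Name the metric. It would help to add that the 95% interval will extend about 0.64 SD of change either side of the estimate.

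Do not simply convert the existing figure to two-sided. That gives .454, which still assumes 40 pairs.

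The cost is protocol wording, with no change to patients, visits or data. The drawback is that the stated detectable effect becomes less favourable.
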